15.0 STATISTICS/DATA ANALYSIS

Statistical Plan:

This is an open label nonrandomized trial to assess the safety and efficacy of subcutaneous abatacept in 10 patients (children and adults) with juvenile onset refractory dermatomyositis (JDM).

We postulate that at least 6 of 10 patients with JDM will meet the myositis preliminary definition of improvement (DOI) after receiving 24 weeks of therapy with abatacept. Data will be entered and stored in the RedCap database, licensed to George Washington University. Primary analyses will be performed using intention to treat regardless of compliance with therapy or trial protocol. We will also perform analyses that include only those participants with known outcome data.

Summary statistics will be generated to describe the study samples. Descriptive statistics, including measures of central tendency (e.g. means, medians) and estimates of spread (e.g. standard deviations) will be used for continuous variables, including reporting of adverse event frequencies, core set measure assessments, and demographic and clinical variables. Non-parametric Wilcoxon signed rank tests will be used to investigate changes in continuous variables. 95% confidence intervals will be calculated for all point estimates.

We will examine the percentage of subjects meeting the DOI (20%), as well as moderate (DOI 50%) or major improvement criteria (DOI 70%), as well as frequency of patients achieving clinically inactive disease.

Due to the small number of subjects, it is unlikely that any statistical test would have the power to detect significant differences in any of the measured variables. We will therefore look not only at the percentage of subjects meeting improvement criteria by the DOIs, but also look for an improvement in individual core set myositis disease activity measurements of muscular and extra-muscular disease activity, as well as the in the patient-reported outcome measures, cutaneous assessments and MRI. We will also examine responsiveness after treatment using standardized response means and correlation degree of change between the measures. Differences between initial

and 24 weeks values will be analyzed by Student t distribution and Wilcoxon matched pair tests.

Statistical analyses will be performed by using GraphPad InStat version 3.00 for Windows 95 (GraphPad, San Diego, CA) and/or SAS System for Windows, version 9.1.3 (SAS Institute, Cary, NC). For all statistical tests, a P-value of < 0.05 will be utilized to indicate statistical significance.

Results of this project may lead to the development of larger study that will have the statistical power to detect significant differences in the measured variables after treatment of JDM with abatacept.

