2.1 PRIMARY OBJECTIVE

AIM: To assess the safety and efficacy of subcutaneous abatacept in an open-label trial of refractory JDM in 10 adults and children.

- **Hypothesis A: *Abatacept will be well-tolerated and safe in treatment–refractory JDM patients.*** For this, the NCI Common Terminology criteria version 4.0 June 2010 will be applied. Medical records will be reviewed for the 6 months prior to enrollment to obtain adverse events prior to beginning abatacept, which will be compared to any adverse events that develop after abatacept was initiated. Particular attention will be given to serious adverse events and infections. Patient evaluations will include: vital sign measurement, physical examination, and laboratory parameters for hematology and routine chemistries.
- **Hypothesis B: *Patients will clinically improve after treatment with abatacept.*** We hypothesize that at least 6 of 10 patients will meet the myositis preliminary definition of improvement after receiving 24 weeks of therapy with abatacept.

Definitions of improvement (DOIs) for clinical trials in IIM have recently been proposed by the IMACS Group (International Myositis Assessment and Clinical Studies) for adult and pediatric myositis utilizing six core set measures among five domains of myositis disease activity (38) (**see Appendix C**). They are:

- a) Physician global disease activity;
- b) Parent/patient global disease activity;
- c) Muscle strength, utilizing manual muscle strength testing (MMT8);
- d) Physical function assessment using the (Childhood) Health Assessment Questionnaire (CHAQ);
- e) Laboratory assessment using the most abnormal serum muscle enzyme level; and
- f) Extra-muscular disease activity using the Myositis Disease Activity Assessment Tool (MDAAT). (see section 14.0: assessment tools: description) (39)

For this clinical trial, the primary endpoint will be the published Definition of Improvement (DOI): 3 of any of the 6 core set measures improved by $\geq 20\%$, with no more than 2 of the core set measures worsening by $\geq 25\%$ (worsening measures cannot include the muscle strength). (Appendix D1) (38)

The PRINTO Group (Pediatric Rheumatology International Trials Organization) has developed and validated a core set of outcome variables for the evaluation of response to therapy in JDM. (40) (Appendix C)

The additional PRINTO core set activity measures are:

- 1) Childhood Myositis Assessment Scale is used as a measure of strength;

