3.1 ENDPOINTS

Primary

The *primary endpoint* of this trial is to establish safety and efficacy of Abatacept in patients with refractory Juvenile Dermatomyositis

- a) Safety: Abatacept will be well-tolerated and safe.
- b) Improvement in myositis disease activity: the published IMACS myositis definition of improvement will be achieved in at least 6 of 10 patients at the end of the trial (38).

Secondary

- a) To evaluate the response rate to Abatacept in JDM using the PRINTO definition of improvement, including criteria for minimal, moderate and major clinical response (40, 41).
- b) To evaluate the response rate to Abatacept using newly developed criteria for myositis clinical response, which are pending ACR-EULAR approval (Appendix D2), as well as other top performing criteria considered at the International Myositis Response Criteria Consensus Conference.
- c) To examine response to treatment in individual core set measures of disease activity as developed by IMACS, including physician and patient/parent global activity, muscle strength (by manual muscle testing), physical function (by HAQ/CHAQ), muscle enzymes, and extra-muscular activity (by the Myositis Disease Activity Assessment Tool)

- d) To examine other core set activity measures as developed by PRINTO, including the Childhood Myositis Assessment Scale, the Disease Activity Score and CHQ-PF50
- e) Steroid-sparing benefit: 20% reduction of the corticosteroid therapy will be achieved in 6 of 10 patients at the end of the trial
- f) To examine improvement in patient reported outcomes, including health-related quality of life and fatigue measures, including the PROMIS and PedsQL fatigue questionnaires. Both patient and parent questionnaires will be obtained, for patients < 18 years of age.
- g) To examine improvement in cutaneous activity, using the Cutaneous Dermatomyositis Area and Severity Index (CDASI) and the Dermatology Life Quality Index, as well as periungual nail fold capillary density. To document changes in cutaneous findings by standardized photography.
- h) To examine improvement in muscle inflammation by examining a thigh/pelvis STIR MRI at baseline and 6 month follow-up. MRI readings will be blinded to the clinical assessment information, including, if possible, date of assessment, and study drug dose.
- i) To examine that disease damage does not increase while under treatment with abatacept, by examining the Myositis Damage Index at baseline and 6 month follow-up.

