- Corticosteroid tapering using the aforementioned guidelines can be commenced at any time on or after week 6 if (a) the patient achieves the DOI and **is rated as at least “mild improvement” compared to the last visit and/or “Moderate improvement” compared to the baseline visit** by both the MD and the patient or parent (for patients less than 18 years of age) or (b) there are complications or circumstances that, in the investigator’s opinion, necessitate the tapering of corticosteroids. The taper schedule is at each visit and the corticosteroid dose will remain stable between study visits. As noted above under Inclusion Criteria #6, it is recommended that patients be on less than 1 mg/kg/day of prednisone at study entry.

Corticosteroid dosing in disease flare:

If in the clinical investigator’s opinion, there are complications or worsening of disease that necessitate an increase in the corticosteroid dose, then the smallest reasonable increase should be considered.

A stable dose of an immunosuppressive (IS) agent must be maintained for a period of 4-6 weeks prior to Visit 1. The dose(s) should be held constant without tapering (unless there is a serious adverse event).

Medications known to induce myositis-like syndromes, including but not limited to, statin agents, fibric acid derivatives, colchicine, and hydroxychloroquine will be subject to the following restrictions. See Tables 1, 2 & 3 below.

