9.0 DISCONTINUATION OF SUBJECTS

Subjects in this study may be discontinued for any of the following reasons:

- Severe allergic reaction to the study medication
- Participation in another investigational drug study
- Any medical condition which, in the opinion of the investigator, warrants discontinuation from the study for the safety of the patient, either as a cause of the study drug or Protocol violations, including non-compliance or inability to perform protocol-required procedures
- Voluntary withdrawal (withdrawal of consent)
- Pregnancy
- Instruct WOCBP to contact the investigator or study staff immediately if they suspect they might be pregnant (e.g., missed or late menstrual period) at any time during study participation. Institutional policy and local regulations should determine the frequency of on-study pregnancy tests for WOCBP enrolled in the study.
- The investigator will notify BMS if a study subject becomes pregnant.
- Loss of ability to freely provide consent through imprisonment or involuntary incarceration for treatment of either a psychiatric or physical (e.g., infectious disease) illness.
- If 3 or more patients develop a serious adverse event thought to be related to study drug, no new patients will be enrolled into the study until the adverse events have been reviewed by the Medical Safety Officer and/or Data Safety Monitoring Board.

Criteria for Disease Worsening (Appendix F):

Criteria for disease worsening in a clinical trial, by which patients could be termed treatment failures and offered alternative therapies, were preliminarily defined by IMACS. They will be incorporated into this trial and include:

- Physician global worsening of ≥ 2 cm on the 10 cm visual analog scale (VAS) and a worsening of the manual muscle testing by $\geq 20\%$, or
- Global extra muscular organ disease activity (a composite of constitutional, cutaneous, skeletal, gastrointestinal, pulmonary and cardiac activity) worsening by ≥ 2 cm on a 10 cm VAS, or
- 3 of any 6 IMACS core set activity measures worse by $\geq 30\%$.

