In order to be classified as “worsening” in this trial, subjects will have to meet the above criteria and be classified by the physician as at least moderately worse (on the Assessment of Study Outcome form). It was also noted by IMACS that significant worsening in cardiac, pulmonary (interstitial lung disease) or GI organs (dysphagia or vasculitis), which, based on the opinion of the treating protocol physician, requires alternate therapy, should be considered as alternate worsening criteria, potentially leading to patients being removed from a trial or considered treatment failures.

All subjects who leave the trial after receiving study drug, regardless of cause, are recommended to obtain a termination evaluation prior to study termination. All patients receiving at least one dose of abatacept will be encouraged to remain in the trial and complete all study visits and phone follow-up evaluations to continue to assess safety.

Continuation of subjects after a serious adverse-event will be based on discussions between the Principal Investigator and Medical Safety Officer and/or Data Safety Monitoring Board. If 3 or more patients develop a serious adverse event thought to be related to study drug, no new patients will be enrolled into the study until the adverse events have been reviewed by the Medical Safety Officer and/or Data Safety Monitoring Board.

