APPENDIX F ACTION PLAN FOR TREATMENT OF WORSENING OF DISEASE:

Criteria for disease worsening in a clinical trial, by which patients could be termed treatment failures and offered alternative therapies, were preliminarily defined at an IMACS Workshop. These criteria will be incorporated into this trial.

. In order to be classified as “worsening” in this trial subjects will have to meet the following criteria:

(1) Physician global worsening of ≥ 2 cm on the 10 cm visual analog scale (VAS) and a worsening of the manual muscle testing by $\geq 20\%$, or

(2) Global extra muscular organ disease activity (a composite of constitutional, cutaneous, skeletal, gastrointestinal, pulmonary and cardiac activity) worsening by ≥ 2 cm on a 10 cm VAS, or

(3) 3 of any 6 IMACS core set activity measures worse by $\geq 30\%$. And

(4) Subjects will have to meet the above criteria and be classified by the investigator as at least moderately clinically worse.

Patients who improve by less than 5% in at least 3 of 6 core set measures by week 12, will be considered to be not improved : These patients may be offered higher dose therapy at 212 mg (87.5 + 125 mg) for subjects with body weight ≥ 50 kg or 137.5 mg for subjects with body weight < 50 kg abatacept weekly.

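### A patient given extra corticosteroid for worsening who then meets DOI counts toward the 6 of 10, and no planned count shows the result without such patients

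*Combined protocol and SAP*

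**What the plan says.** Section 15.0 postulates that at least 6 of 10 patients will meet DOI after 24 weeks. It sets the primary rule, "Primary analyses will be performed using intention to treat regardless of compliance with therapy or trial protocol", and names one other analysis: "We will also perform analyses that include only those participants with known outcome data".

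Section 2.1 builds the DOI by "utilizing six core set measures among five domains of myositis disease activity". Neither that section nor Appendix D1 puts a condition on steroid dose.

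Section 5.0 deals with flare. If the investigator judges that there are "complications or worsening of disease that necessitate an increase in the corticosteroid dose, then the smallest reasonable increase should be considered". It states no consequence for response status.

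Section 9.0 adopts worsening criteria "by which patients could be termed treatment failures and offered alternative therapies, were preliminarily defined by IMACS", and describes organ worsening as "potentially leading to patients being removed from a trial or considered treatment failures". Appendix F repeats the first phrase.

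Section 3.1 lists a separate secondary endpoint: "Steroid-sparing benefit: 20% reduction of the corticosteroid therapy will be achieved in 6 of 10 patients at the end of the trial".

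**The concern.** The trial has a single arm. If a patient worsens, receives more steroid than at baseline and then meets DOI, nothing in the design separates the effect of abatacept from that of the added steroid. The protocol itself treats steroid dose as something to control: it asks for a stable dose before entry and a standardized taper tied to DOI. Only the upward route has no place in the analysis.

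No formal test is attached to 6 of 10, but it is the stated efficacy hypothesis, and Section 15.0 says the results may lead to a larger study. With ten patients, one person is 10 percentage points. Without a rule fixed in advance, a decision about one patient, made after the open-label data are seen, could settle whether the target is called met.

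**Working it through.** **Reading the sections together**

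1. Section 5.0 permits a steroid increase for worsening.
2. Section 9.0 encourages every dosed patient to complete all visits, so a week-24 DOI can be observed after the increase.
3. The DOI has no steroid term, so such a patient can meet it.
4. The intention-to-treat count includes the patient. The known-outcome count does too, because the outcome is known.
5. The treatment-failure wording is optional. It needs formal thresholds plus at least moderate worsening by the physician, or organ worsening that requires other therapy. A steroid increase under Section 5.0 needs neither, and Section 15.0 never refers to treatment failure.
6. The steroid-sparing endpoint is counted separately. A patient can fail it and still be a DOI responder.

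The route is mainly steroid. Section 5.3 bars biologics and holds the IVIG regimen stable, and Section 5.0 holds immunosuppressant doses constant.

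**The plan's own figure**

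At least 6 of 10 is postulated without a null rate, design rate or power, so there is no calculation to reproduce. Clopper-Pearson 95% intervals are 26.2-87.8% for 6/10 and 18.7-81.3% for 5/10.

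**Size (all rates assumed)**

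- p0, DOI rate on abatacept without added steroid: 0.30, 0.40 or 0.50.
- r, share of the remaining patients given more steroid: 0.05 to 0.20.
- c, share of those who then meet DOI: 0.10 to 0.30.

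Apparent rate: π = p0 + (1 − p0) × r × c. 
Chance of reaching the target: P(X ≥ 6) for X ~ Binomial(10, π). 
Chance of at least one such responder: 1 − [1 − (1 − p0) × r × c]^10.

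At p0 = 0.40:
- Low end: 0.60 × 0.05 × 0.10 = 0.003, so π = 0.403 and P(X ≥ 6) = 0.1713. At least one such responder: 1 − 0.997^10 = 0.030.
- High end: 0.60 × 0.20 × 0.30 = 0.036, so π = 0.436 and P(X ≥ 6) = 0.2326. At least one such responder: 1 − 0.964^10 = 0.307.

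| p0 | P(X ≥ 6) at p0 | Apparent rate | P(X ≥ 6) at apparent rate | At least one such responder |
|---|---|---|---|---|
| 0.30 | 0.0473 | 0.3035-0.342 | 0.0500-0.0858 | 0.034-0.349 |
| 0.40 | 0.1662 | 0.403-0.436 | 0.1713-0.2326 | 0.030-0.307 |
| 0.50 | 0.3770 | 0.5025-0.530 | 0.3831-0.4526 | 0.025-0.263 |

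One such patient turns 5/10 into 6/10 only when exactly five others respond. The chance of exactly five responders without added steroid is 0.103, 0.201 and 0.246 at p0 = 0.30, 0.40 and 0.50.

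**Cost of scoring these patients as non-responders**

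Suppose a share d of patients who would have responded to abatacept alone had a steroid increase first. The rate in the supportive count is p0 × (1 − d). At p0 = 0.40 and d = 0.05, 0.10, 0.20 this is 0.38, 0.36, 0.32, and P(X ≥ 6) is 0.1348, 0.1072, 0.0637.

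Compared with 0.1662, the present rule adds 0.0051 to 0.0664 (0.1713 − 0.1662; 0.2326 − 0.1662). The alternative scoring removes 0.0314 to 0.1025 (0.1662 − 0.1348; 0.1662 − 0.0637).

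**The case against.** Scoring the observed DOI whatever else was given is a recognised treatment-policy choice. It suits a trial in which steroids and immunosuppressants are part of the background. The intention-to-treat sentence speaks of compliance, and a flare increase is permitted by the protocol, so the sentence is not a rule about rescue. The pathway is narrow: a patient with intolerance or inadequate response to prednisone (inclusion item 5a) must worsen, receive a deliberately small increase, and still finish at least 20% better than baseline on three of six measures. Dropping such patients does not restore attribution either, because no responder in a single-arm trial with background therapy can be attributed with confidence. Steroid change is already a secondary endpoint, and the alternative scoring can move the result more than the bias it addresses.

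Most of this stands. It is a good reason not to replace the primary count. It does not remove the gap: neither planned count shows whether 6 of 10 was reached without added steroid, and no cross-listing of DOI with steroid change is planned.

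Two stronger readings are tempting. A reader might infer that the protocol declares rescued patients to be responders, or that the treatment-failure wording contradicts Section 15.0. The documents support neither. The first follows only from combining sections, and the failure wording is permissive and unconnected to the DOI count. Nor do they support calling the intention-to-treat rule an error.

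**Conclusion.** The gap is real and minor. A patient given above-baseline steroid for worsening can count toward the 6 of 10, and no planned analysis shows the count without such patients.

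The effect is probably small and may be negligible. At the low end of the assumed range the chance of reaching the target rises by 0.003 to 0.006 across true rates of 30% to 50%. At the high end and a true rate of 40% it rises by 0.066. The low end is more plausible, given the refractory population and the small increase that Section 5.0 calls for. Every rate is an assumption. A reader might infer that the efficacy result would be materially inflated; the documents give no rescue frequency that would support this.

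**What to change.** Amend Section 15.0 only; dosing, rescue, stopping and extension rules stay as they are.

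- Keep the intention-to-treat DOI count as primary.
- Beside it, report a prespecified supportive count over all treated patients. Score as non-responder anyone who, for disease worsening before the week-24 assessment, received corticosteroid above the baseline dose or a new or increased myositis agent.
- Do not score as non-response the week-12 abatacept escalation, or a return to no more than the baseline steroid dose after a taper.
- List every patient with any above-baseline steroid, with dose, timing, reason and DOI status, so that the result does not rest on the investigator's attribution alone.
- State whether 6 of 10 is met on both counts.

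The cost is one paragraph and one listing. Section 7.1 already has concomitant medication reviewed and recorded at each follow-up visit; a field for the reason for a steroid increase may be needed. The downside is that the supportive count may understate response, because a patient who would have responded to abatacept alone can be scored as a non-responder. That is why it stands beside the primary count and does not replace it.

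### Section 15 has no scoring rule for patients who stop abatacept or switch therapy, so the primary ITT count as written could credit another treatment's response toward the 6 of 10

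*Combined protocol and SAP*

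**What the plan says.** Section 2.1 (Hypothesis B) expects that "at least 6 of 10 patients will meet the myositis preliminary definition of improvement after receiving 24 weeks of therapy with abatacept". Section 15 repeats the condition ("after receiving 24 weeks of therapy with abatacept"). Section 3.1 states the endpoint without it: "the published IMACS myositis definition of improvement will be achieved in at least 6 of 10 patients at the end of the trial".

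Section 15 gives two instructions on who is analysed:

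- Primary: "Primary analyses will be performed using intention to treat regardless of compliance with therapy or trial protocol".
- Supportive: "We will also perform analyses that include only those participants with known outcome data".

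Section 9 lists grounds for discontinuation, among them severe allergic reaction, pregnancy and non-compliance. It then adopts worsening criteria "by which patients could be termed treatment failures and offered alternative therapies"; Appendix F repeats them. For serious cardiac, pulmonary or gastrointestinal worsening that needs other treatment, Section 9 describes the consequence as "potentially leading to patients being removed from a trial or considered treatment failures". It also says: "All patients receiving at least one dose of abatacept will be encouraged to remain in the trial and complete all study visits". The stated purpose of that follow-up is safety.

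No section says how a patient who stopped abatacept, switched, or was called a treatment failure enters the DOI count.

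**The concern.** The question is tied to a full course of abatacept, while the analysis rule sets adherence aside. A patient could stop after a few doses because of an allergic reaction, start another immunosuppressant, attend week 24 and meet the DOI. Nothing in Section 15 prevents that patient from counting toward the 6 of 10. The supportive analysis does not remove the patient either, provided a week-24 outcome exists.

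In a randomised trial, an ITT comparison is anchored by a control arm in which later therapies are also available. Here there is none, so improvement on a later drug cannot be separated from improvement on abatacept. Any such credit would come from patients in whom abatacept failed or was not tolerated. With 10 patients, one of them is 10 percentage points, or 1/6 (17%) of the target.

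**Working it through.** **Is the route open?**

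1. Patients can leave abatacept before week 24 (Section 9).
2. Alternative therapy is foreseen (Section 9, Appendix F).
3. Week-24 core set measures can exist for them, because continued visits are encouraged (Section 9) and Visit 5 collects the full core set (Section 7.1). This is possible but not assured: Section 9 only recommends a termination evaluation for those who leave, and Visit 5 doubles as the early-termination visit.
4. Section 15 contains no rule that would score such a patient as a non-responder.

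**Does other text close it?** The treatment-failure wording is the only candidate. It says patients could be so termed, not that they will be. It applies to worsening, so stopping for allergy, pregnancy or non-compliance falls outside it. Neither Section 15 nor the DOI definition in Appendix D1 refers to it.

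**How much could the scoring rule matter?** There is no plan figure to reproduce: 6 of 10 is a postulated count without a null rate or power. The following is a sensitivity calculation. Only the 10 patients and the target of 6 come from the documents. Assumed quantities are the response probability p in patients who stay on abatacept, the number of switchers k, and the switchers' week-24 response probability q.

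- k = 1: P = q·P(Bin(9,p) ≥ 5) + (1−q)·P(Bin(9,p) ≥ 6)
- k = 2: P = q²·P(Bin(8,p) ≥ 4) + 2q(1−q)·P(Bin(8,p) ≥ 5) + (1−q)²·P(Bin(8,p) ≥ 6)

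Setting q = 0 gives non-responder scoring of the same patients. At p = 0.5:

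- P(Bin(9,0.5) ≥ 5) = 256/512 = 0.500; P(Bin(9,0.5) ≥ 6) = 130/512 = 0.254
- P(Bin(8,0.5) ≥ 4) = 163/256 = 0.637; P(Bin(8,0.5) ≥ 5) = 93/256 = 0.363; P(Bin(8,0.5) ≥ 6) = 37/256 = 0.145
- One switcher, q = 0.3: 0.3 × 0.500 + 0.7 × 0.254 = 0.328
- Two switchers, q = 0.3: 0.09 × 0.637 + 0.42 × 0.363 + 0.49 × 0.145 = 0.281

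Chance of at least 6 of 10:

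| p | Switchers | Scored as non-responders | By week-24 state, q = 0.3 to 0.7 | Extreme case, q = 1 |
|---|---|---|---|---|
| 0.5 | 1 | 0.25 | 0.33 to 0.43 | 0.50 |
| 0.5 | 2 | 0.15 | 0.28 to 0.48 | 0.64 |
| 0.6 | 1 | 0.48 | 0.56 to 0.66 | 0.73 |
| 0.6 | 2 | 0.32 | 0.48 to 0.68 | 0.83 |

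Without any switcher the chance is 0.38 at p = 0.5 and 0.63 at p = 0.6.

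On the observed scale, one switcher counted as a responder turns 5/10 into 6/10. The exact 95% intervals, 19% to 81% and 26% to 88%, overlap almost entirely, so the rule alters whether the stated target is met far more than it alters the evidence.

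**The case against.** The strongest reply is that the ITT sentence defines who is analysed, not how the DOI is scored after a switch. The sentence that follows it also concerns the analysis set. A reader might infer that the plan positively scores switchers by their week-24 state. The documents do not say so; that is the ordinary consequence of the ITT sentence when no other rule exists. The treatment-failure wording leans toward non-response, and Section 15 and Section 9 are simply not connected. This part of the reply stands, and it is why the point is an open scoring rule rather than a wrong one.

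Other replies narrow the point without removing it:

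- Leavers may have no assessment after switching. That makes the case less frequent, not impossible.
- Section 5.3 bars other biologics and Section 5.0 holds background immunosuppressants constant. Neither says how a patient who nevertheless changes therapy is scored, and the primary analysis explicitly includes protocol deviators.
- Pregnancy or non-compliance does not itself imply a new myositis drug. True; the allergy and worsening routes are the more relevant ones.
- Counting outcomes whatever was taken is a legitimate choice, and it keeps early stoppers in the denominator, which is conservative. It answers a different question from Hypothesis B, however, and the proposed rule keeps the same denominator.
- The target carries no formal decision rule and the plan concedes low power. That limits the consequence, although Section 15 says the results may lead to a larger study.

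**Conclusion.** The concern holds as a missing rule. Section 15, read with Section 9 and Appendix F, leaves open whether a patient who left abatacept can count as a responder, and its only primary instruction leans toward yes. No planned analysis is confined to responses achieved on abatacept, which is what Hypothesis B asks about.

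At an assumed on-drug rate of 50%, the scoring choice changes the chance of reaching 6 of 10 from 0.25 to between 0.33 and 0.43 with one switcher, and from 0.15 to between 0.28 and 0.48 with two. The values of p, k and q are all assumptions; the documents give no discontinuation or switching rate.

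A reader might infer a larger inflation, from 0.38 with no switchers to 0.50 or 0.64 with one or two. That requires every switcher to respond, which nothing in the documents supports for a refractory population, and it compares different patient mixes instead of the same patients under two rules. At q = 0.3 the week-24 figures (0.33 and 0.28) in fact lie below 0.38.

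Steroid increases in patients still on abatacept are a separate matter and are not part of this point.

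**What to change.** In Section 15:

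1. Keep all 10 patients in the denominator of the primary DOI count.
2. Count as a primary responder only a patient who meets the DOI at week 24 and has neither permanently stopped abatacept nor started an alternative myositis therapy before that visit.
3. Score all others as non-responders, including those termed treatment failures and those without a week-24 assessment.
4. Report the count made irrespective of adherence beside it, as supplementary.
5. Reconcile this text with the treatment-failure wording in Section 9 and Appendix F, so that it is clear what the label means for the DOI count.

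This takes a few sentences and uses data already collected: the medication administration log (Section 10) and the concomitant-medication review at each follow-up visit (Section 7.1). It changes no dose and no clinical rule. The cost is that the headline count can only stay equal or fall. A patient who had improved on abatacept but stopped for an unrelated reason would count as a non-responder; the supplementary count would show that patient.
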